### Subject Risks and Benefits

#### *Possible Benefits:*

As this is an open-label study, all participants will receive treatment with erenumab. It is likely that many patients will have improvements in their migraine patterns following treatment with erenumab, as has been demonstrated in the phase II and III clinical trials and by the US Food and Drug Administration approval.

#### *Possible Risks:*

The most common side effects are injection site reaction, constipation, muscle spasm and pruritis. With the exception of injection site reaction (5.2%), these side effects were reported by less than 5% of patients in the phase II and III clinical trials. Constipation, sometimes with serious complications, was reported by approximately 3% of individuals receiving erenumab.

Development of hypertension and worsening of pre-existing hypertension have been reported following the use of AIMOVIG in the postmarketing setting. Many of the patients had pre-existing hypertension or risk factors for hypertension. There were cases requiring pharmacological treatment and, in some cases, hospitalization. Hypertension may occur at any time during treatment but was most frequently reported within seven days of dose administration. In the majority of the cases, the onset or worsening of hypertension was reported after the first dose.

The FDA has added a safety-related label change to erenumab to include a contraindication for patients with serious hypersensitivity to erenumab or to any of the excipients due to the risk of anaphylaxis and angioedema. Most hypersensitivity reactions were not serious and occurred within hours of administration, although some occurred more than one week after administration.

Hypersensitivity reactions including rash and swelling/edema have been reported with erenumab in postmarketing experience.

Additional risks that have been reported since erenumab was approved in May 2018 include mouth/lip sores and skin and subcutaneous tissue disorders such as alopecia and rash.

Potential risks associated with erenumab use during pregnancy and lactation are not established.

Protected health information (PHI) is being collected. Although measures are taken to reduce the risk, it is possible that there could be inappropriate access to the PHI by individuals not approved for such access.

#### *Protection Against Risks:*

Individuals who are known to be pregnant or lactating will be excluded from study participation. Women of childbearing potential who are not known to be pregnant will have urine pregnancy testing before the 4 week run-in phase and prior to each of the two erenumab treatments. Women found to be pregnant will not receive any additional treatments with erenumab. Women of childbearing potential will be required to use a reliable form of contraception from the start of the run-in phase through 16 weeks after the last dose of erenumab (details provided in 'eligibility criteria' section of this protocol).

Measures that will be taken to protect PHI: All information collected from study participants will be locked in a secure location. Identifying information will be removed from the data forms and replaced by unidentifiable codes. Electronic databases/spreadsheets will be password protected and only accessible to those with access rights. Data will be entered into REDCap. (43) REDCap is a secure web-based application used for designing and managing clinical research databases. REDCap's design addresses the National Center for Research Resources statement that the future of biomedical research will involve collaborations amongst many scientists in different locations linked by high-speed computer networks thus enabling data submission, data sharing and data analyses. (43, 44) REDCap is accessible to study investigators via any computer with a Web browser. Once data are entered into data collection forms, data automatically upload to the registry data file. The registry complies with all HIPAA regulations, requires a log-in ID and password, and users only have access to specific functions (e.g. view data, add data, change data, etc.) once granted rights for those specific functions. Data can be exported into numerous formats utilized by several frequently used statistical packages including SPSS, SAS, R, Excel, Stata and others.

#### Subject Retention

Subject retention and diary compliance will be essential for study success.

At the time of considering an individual for participation in this study, it will be ensured that the individual will be available for the duration of the study. The responsibilities of the subject will be clearly defined. All research visits will be scheduled at the time of enrollment. Subjects will be contacted with reminders prior to each research appointment.

Diary compliance will be monitored on a daily basis. Subjects will be contacted immediately if non-compliance is observed. Individuals who have diary compliance less than 80% during the run-in phase will be withdrawn from the study.

#### Analysis Plans

*Specific Aim #1 (i.e. identify changes in brain structure and function that correlate with response to erenumab):* Pre-treatment and post-treatment MRI data will be used for within and between subject

comparisons. Within subject analyses will compare baseline brain activation and perfusion patterns and functional connectivity patterns pre-treatment to post-treatment. Between subject group analyses will compare post-treatment MRI data in erenumab responders to non-responders.

Similar comparisons will be made for pre- and post-treatment pain thresholds (i.e. results of quantitative sensory testing) and cognitive testing.

So as to help with the interpretation of differences between responders and non-responders, MRI data from erenumab-treated patients will be compared to healthy non-migraine control data that we have already collected during the conduction of previous studies, when available (although we have plenty of data for the majority of analyses, we have limited ASL data and no n-back data from healthy controls). Differences in brain structure and function of migraine patients prior to erenumab treatment compared to healthy controls will be identified. Results of this analysis will determine alterations of brain structure and functions in migraine patients compared to healthy controls. Areas where migraine patients show altered structure and function will be used as regions of interest (ROIs) to assess the longitudinal, within-group changes of erenumab responders and non-responders.

Although multiple analyses are planned using functional, structural, and perfusion data, the primary analysis for specific aim #1 will be the comparison of pre-treatment pain-induced regional activation strength vs. post-treatment pain-induced regional activation strength in erenumab responders and separately in erenumab non-responders.

Post-treatment changes in other measures of brain function as well as measures of brain perfusion, brain structure, cutaneous pain thresholds and cognitive function in those responding to erenumab and in those not responding will be explored.

Two-tailed T-Tests or Mann-Whitney U tests will be used to perform group comparisons on demographic and cognitive measures and on pain threshold data. Neuroimaging data will be analyzed using general linear model designs. Within-group changes on cognitive measures, sensory testing and neuroimaging data will be assessed by applying a general linear mixed model design.

*Specific Aim #2 (i.e. Develop models to predict which patients will respond to erenumab):* Pre-treatment scans will be used to identify MRI predictors of erenumab response. Multivariate machine-learning modeling of brain structural and functional data will be utilized for developing the predictive model. Because there are many imaging features available, but only a limited set of patients for this analysis, principal components analysis (PCA) will be performed on features collected from each imaging type to reduce the dimensionality of the data. The principal components (PCs) that result from PCA are linear combinations of the original imaging features, and can consolidate the information from the original features in such a way that only a few PCs are needed to explain most of the data variance. PCA will be performed separately on features from each imaging type to enhance clinical interpretability of PCs chosen for the predictive model.

To maximize the prediction accuracy, we will employ an ensemble learning approach by including a number of contemporary and complementary machine learning algorithms for building the predictive model, including Linear Discriminant Analysis (LDA), Quadratic Discriminant Analysis (QDA), Support Vector Machines (SVM), and Decision Tree (DT). Integrating these algorithms with Particle Swarm

Optimization (PSO)-based feature selection, we will identify the subset of features (PCs) that maximizes cross-validated accuracy of predicting responders and non-responders. Feature selection is a key step to avoid overfitting when building a predictive model with limited samples. PSO is a bio-inspired optimization algorithm that mimics the collective and collaborative behavior of social swarms in nature, e.g., colonies, honeybees, and bird flocks, in finding the optimal feature subset, and has been shown to outperform conventional feature selection algorithms in numerous recent publications.

Additionally, noting that this study will collect both widely accessible imaging data such as that derived from T1-weighted sequences as well as less accessible types such as pain-induced functional activations, we aim to determine how widely useable our predictive model is in clinical practice. To achieve this goal, we will first limit our PSO-based feature selection to select only PCs derived from structural measures of T1-weighted sequences. Then we will compare the accuracy to that of another analysis allowed to select resting state functional connectivity data, followed by selection of additional PCs from more advanced imaging data. This result will help determine how much value is added when using advanced imaging data in predicting treatment response; and if advanced imaging is not available in a clinic, how good the predictive accuracy can be.

Patient characteristics, cognitive function, and sensory thresholds can also be included in predictive models.

*Safety Analysis:* The proportion of subjects experiencing adverse events, the nature of the adverse events, as well as severity and relationship of the adverse events to the study will be reported using descriptive statistics. The proportion of subjects with adverse events that led to withdrawal from the study will also be reported. All subjects who received at least one dose of erenumab will be included in the safety analysis.

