## **Summary**

Compared to healthy people without migraine, migraine is associated with alterations in brain structure and function. This is a prospective, longitudinal, open-label study that will investigate brain magnetic resonance imaging changes amongst individuals with migraine following treatment with erenumab.

The Specific Aims of this study are to:

- 1. Identify changes in brain function and structure that correlate with response to erenumab.**
- 2. Develop models using imaging data to predict which patients will respond to erenumab.**  
Pre-treatment and early post-treatment imaging data will be used separately for predictive modeling.

The study will include 50 subjects with migraine aged 18-65 years who have 6-25 migraine days per month at baseline. Following a 4-week run-in phase, subjects will be treated twice with once monthly subcutaneous injections of erenumab 140 mg. Questionnaires, structured interviews, cognitive tests, quantitative sensory testing and brain imaging will be performed prior to and following erenumab treatment. These data will be collected at early time points after the first treatment as well as at eight weeks following the first treatment to allow for identification of early and late effects of erenumab on clinical, physiologic, and imaging outcomes and to determine if early physiologic and imaging outcomes predict clinical outcomes at eight weeks. Physiologic and imaging data will be compared to already collected data from healthy controls so as to interpret changes that are seen following treatment with erenumab.

The primary hypothesis is that improvements in migraine patterns associated with erenumab treatment will be associated with “normalization” of brain function. Secondarily, it is hypothesized that improvements in migraine patterns associated with erenumab treatment will be associated with “normalization” of brain structure, pain thresholds, and cognitive performance. Finally, it is hypothesized that exploratory analyses will demonstrate that there are early changes in brain function following the first treatment with erenumab and that these early changes will be predictive of longer-term clinical responsiveness to erenumab.

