(Wellcome Department of Cognitive Neurology, Institute of Neurology, London, UK) and the toolbox DPARSF interfaced with MATLAB version 11.0 (MathWorks, Natick, Ma, USA).(33) Rs-fMRI data will be pre-processed using standard procedures including the following steps: slice-time correction, motion correction, re-alignment, skull and non-brain tissue removal, spatial smoothing, and alignment to an average Montreal Neurological Institute (MNI-305) template.(34, 35) Further post-processing steps will include band-pass filtering, as well as removal of variance related to head motion, white matter signal and cerebrospinal fluid signal. Functional measurements will be imported into SPSS 21.0 (SPSS Inc, Chicago, IL) for further calculations. A region-of-interest approach will be utilized for functional connectivity analyses. The functional connectivity of 33 regions which commonly participate in pain-processing will be analyzed. Event-related BOLD data will be analyzed using a whole-brain analysis, comparing BOLD amplitude during painful stimuli vs. no stimuli. All preprocessing and general linear model (GLM) estimation of brain activation patterns for the event-related portion of the fMRI will also be performed using SPM8, interfaced with Matlab. Functional images will be realigned to the mean volume in the series, motion-corrected, realigned to each individual's structural images, normalized to standard stereotaxic space (Montreal Neurological Institute template) and smoothed using a 5 mm full width half maximum Gaussian kernel. Brain regions activated in response to painful stimuli will be identified by generating contrast maps representing brain activations associated with painful stimuli preceded by auditory cue vs. auditory cue with no painful stimuli. The BOLD signal will be modeled for each of eight successive MR frames (20 seconds) following stimulus presentation, with no assumption made about the shape of the hemodynamic response function. These contrast maps are entered into a mixed effects analysis. A main effects analysis will identify brain regions activated in subjects and a two-sample analysis will identify regions differentially activated when comparing subject cohorts. Cluster threshold correction and multiple comparisons correction will be utilized. 18 major fiber tracts will be reconstructed from DTI data using an automated technique based upon global probabilistic tractography (TRACULA).(36) This software toolbox is available online (<http://surfer.nmr.mgh.harvard.edu/>) and uses anatomical priors (T1-weighted data) as input. The robustness of the TRACULA software algorithm has been validated in prior papers.(36, 37) For each of the 18 fibertracts, tract volume, path length, axial diffusivity, radial diffusivity, mean diffusivity, and fractional anisotropy will be calculated. Arterial Spin Labeling data will be analyzed using SPM 8 and the toolbox ASLtbx.(38) SPM 8 and ASLtbx are freely downloadable online and will be interfaced with MATLAB version 11.0. ASL data will be preprocessed using standard SPM preprocessing steps including orientation resetting, image reorienting, motion correction, and co-registration (of each subjects' T1-weighted image with the ASL images) and data smoothing. Subsequent data post-processing steps will be conducted using the ASLtbx toolbox. Statistical analyses will be conducted using a GLM design.

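### Aim 1 names no test of whether brain change differs between responders and non-responders, and its ROI-based pre/post tests lean slightly toward 'normalisation'

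*Combined protocol and SAP*

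**What the plan says.** Under Specific Aim #1, Analysis Plans makes the primary analysis "the comparison of pre-treatment pain-induced regional activation strength vs. post-treatment pain-induced regional activation strength in erenumab responders and separately in erenumab non-responders". The only between-group test of the imaging data that it describes for the two response groups is "Between subject group analyses will compare post-treatment MRI data in erenumab responders to non-responders". The Background section goes further: it says longitudinal changes in responders will be set against those in non-responders. Specific Aims frames Aim 1 as finding changes that correlate with response.

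On regions, Analysis Plans says "Differences in brain structure and function of migraine patients prior to erenumab treatment compared to healthy controls will be identified", and then "Areas where migraine patients show altered structure and function will be used as regions of interest (ROIs) to assess the longitudinal, within-group changes". Table 1 schedules MRI at baseline, week 2 and week 8, so there is one pre-treatment scan.

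Imaging Data Plans says "Event-related BOLD data will be analyzed using a whole-brain analysis, comparing BOLD amplitude during painful stimuli vs. no stimuli". For that analysis it adds "Cluster threshold correction and multiple comparisons correction will be utilized", without a method or level. It names a region-of-interest method for one modality only: "A region-of-interest approach will be utilized for functional connectivity analyses". The Summary opens its hypotheses with "The primary hypothesis is that improvements in migraine patterns associated with erenumab treatment will be associated with" normalised brain function.

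**The concern.** There are two linked problems.

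**The question in Aim 1 has no matching test.** A significant change in responders beside a non-significant one in non-responders does not show that the changes differ. A difference between post-treatment scans may have been there before treatment. Aim 2 itself looks for pre-treatment imaging differences that predict response. A report built on these tests could therefore call a region a marker of response when it changed equally in both groups or never changed.

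**The ROI step reuses data.** A region that enters the list partly because baseline noise pushed it away from controls will drift back on rescan with no drug effect. That drift is in the hypothesised direction. It affects responders and non-responders alike, and the study has no untreated arm that would reveal it.

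**Working it through.** **Inputs from the protocol.** 21 responders and 21 non-responders, a BOLD difference of 0.1%, SD 0.1, type I error 0.05 and stated power 88% (Sample Size); 50 controls (Participants); one pre-treatment scan (Table 1).

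**Inputs assumed, because the protocol gives none.** Test-retest reliability r of 0.3 to 0.9; ROI selection at two-sided p<0.05, p<0.05/33 or p<0.001. The figure 33 is borrowed from the number of connectivity regions and is illustrative for pain activation.

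**1. The plan's own figure.** Two-sample t test, 21 per group, standardised difference 0.1/0.1 = 1, df 40, noncentrality 1 × √(21/2) = 3.24: power 88.5%, against 88% stated. A paired t test in 21 with SD of change 0.1 gives 99.2%. The stated 88% is therefore what an unpaired comparison of 21 with 21 delivers. If 0.1% is the SD of change, that is the power of the contrast of change.

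**2. What the named tests estimate.** Let P be a group's mean at baseline and C its mean change, for responders (R) and non-responders (N).
- Within-group tests: C_R, and separately C_N.
- Post-treatment comparison: (P_R + C_R) − (P_N + C_N).
- Aim 1 needs C_R − C_N.

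The post-treatment comparison equals the last line only if P_R = P_N.

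Illustration: both groups truly change by the same 0.05% (half the design effect), with SD of change 0.1%. Paired power in 21 is 58.7%. The groups are different patients, so the chance of significance in responders only is 0.587 × 0.413 = 24%. About one trial in four would then look response-specific for that region when the changes are identical. The contrast of change would be significant in 5%.

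**3. ROI selection.** Simulation with 42 patients, 50 controls, SD 1 per scan and no treatment effect. A region is kept if the baseline two-sample t test passes the threshold; a paired t test is then run in 21 responders. Ranges run over r = 0.3, 0.5, 0.7 and 0.9.

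| True patient-control difference | Selection | Regions kept | Error toward controls (nominal 2.5%) | Two-sided error (nominal 5%) |
|---|---|---|---|---|
| 0 | p<0.05 | 5% | 4.1-9.5% | 5.4-9.7% |
| 0 | p<0.001 | 0.1% | 5.6-17.2% | 6.6-17.3% |
| 0.5 SD | p<0.05 | 66% | 2.8-3.6% | 4.8-5.1% |
| 0.5 SD | p<0.05/33 | 20% | 3.6-5.2% | 5.3-6.0% |
| 0.5 SD | p<0.001 | 17% | 3.6-5.9% | 5.3-6.6% |
| 1 SD | p<0.05 | 99.7% | 2.4-2.6% | 4.8-5.1% |
| 1 SD | p<0.05/33 | 93% | 2.5-2.8% | 4.7-5.1% |
| 1 SD | p<0.001 | 91% | 2.5-2.7% | 4.6-5.0% |

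At p<0.05/33 about 0.15% of null regions pass, with error toward controls of about 5-17%. Simulation error is about 0.1 percentage point in most rows (√(0.025 × 0.975/20,000) = 0.0011). It is larger in the strict null row, which has about 4,000 regions per cell.

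The largest spurious mean shift is 0.013 SD at a true difference of 1 SD, 0.117 SD at 0.5 SD and 0.279 SD in null regions. If 0.1% is the SD per scan, these are about 0.001%, 0.012% and 0.028% BOLD, against the 0.1% design effect.

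**4. Contrast of change in the selected regions.** Two-sample t test on post minus pre, responders against non-responders: error 4.4-5.5% in every cell. Selection pools all patients, so the drift is the same in both groups and cancels.

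**5. Power of the contrast, 21 v 21.** If 0.1% is the SD per scan, the SD of change is 0.1% × √(2(1 − r)).

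| r | SD of change | Difference 0.1%, one region | Difference 0.1%, Bonferroni over 33 | Difference 0.05%, one region |
|---|---|---|---|---|
| 0.3 | 0.118% | 76% | 27% | 27% |
| 0.5 | 0.100% | 89% | 45% | 35% |
| 0.7 | 0.077% | 98% | 77% | 53% |

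**The case against.** **A reader might infer that the primary analysis is circular.** The documents do not support that. Imaging Data Plans puts event-related BOLD in a whole-brain analysis with correction, and names an ROI approach only for connectivity. Analysis Plans introduces the control comparison as an aid to interpretation and calls the other measures exploratory. What stands is an ambiguity: the ROI sentence covers function as well as structure, and the primary analysis speaks of regional activation without naming regions.

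**A reader might also infer a large inflation of false positives.** The high figures apply only to regions with no true difference that were nevertheless selected, and strict thresholds let very few of those through. The protocol reports earlier patient-control differences in activation, connectivity and structure, so a wholly null set is a worst case. At 0.5 SD with p<0.05 selection, errors mostly move from one tail to the other and two-sided error stays near 5%.

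**The comparison of change is arguably intended.** The Background section describes it. The diary section says correlations between change in migraine frequency and imaging could be assessed. Imaging Data Plans mentions a two-sample analysis of cohorts, and a mixed model is planned. This stands as to intent. But the mixed model is described for within-group change, the two-sample analysis compares activation maps and does not mention change, and the correlations are optional. No section commits to the test.

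**Replacing cohort-derived ROIs has a price.** The team's earlier heat-pain study was in episodic migraine, while this trial also enrols chronic migraine. That objection stands, and it is why the fix keeps the ROIs.

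**Conclusion.** The main gap is that Aim 1 asks whether change goes with response, and no specified test answers it. This follows from the text and needs no assumption. The 24% illustration assumes an equal true change of 0.05% in both groups and an SD of change of 0.1%.

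The ROI bias is real and runs toward the hypothesis, but it is modest. It is negligible at a true difference of 1 SD, about 3-6% against 2.5% at 0.5 SD, and larger only in regions that have no true difference. These sizes depend on the assumed reliability and thresholds, and on selection using all patients pooled. Whether the bias reaches the primary test cannot be settled from the documents; Imaging Data Plans suggests that it does not.

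**What to change.** 1. In Analysis Plans, name the responder-versus-non-responder contrast of pre-to-post change as the test of Aim 1. It is the group-by-time term in the mixed model already planned; say which post-treatment scan it uses. It needs no new data. Its power is 88.5% for one region if 0.1% is the SD of change, and lower if the groups differ by less or after correction over many regions (working, step 5). It shows association with response; in a single-arm study it does not show a drug effect.

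2. Keep the baseline-derived ROIs, and add a sensitivity analysis of the within-group tests in regions fixed independently of this trial's baseline scans. The team's earlier studies are one source, with the caveat that the heat-pain study was in episodic migraine. State that within-group change in baseline-selected ROIs will not, on its own, be read as evidence of normalisation. The cost is a region list and one extra set of analyses.

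3. State whether the primary pain-activation test is whole-brain or ROI-based, and reconcile Analysis Plans with Imaging Data Plans. If it is whole-brain, say that the baseline-derived ROIs do not restrict it. This is a change of wording only.

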## **Background**

Migraine is a highly prevalent disorder that affects 38 million people in the US and is associated with moderate to severe pain, hypersensitivities to sensory stimuli, nausea, vomiting, and reduced quality of life. (1-3) Annual costs from migraine are estimated at \$20 billion in the United States and €27 billion in Europe. (4, 5) Migraine remains poorly treated and there are currently few options for the preventive treatment of migraine. The release of erenumab to the market represents a substantial improvement in the landscape of migraine preventive treatment.

Phase 2 and 3 randomized, double-blind, placebo-controlled studies have demonstrated that erenumab is safe and effective for the prevention of episodic and chronic migraine. (6-8) Erenumab received US Food and Drug Administration approval for the prevention of migraine in May 2018. Structural and functional neuroimaging could provide important insights into central mechanisms of treatment response and imaging biomarkers that track treatment response or are indicators for early treatment response. A few studies have demonstrated normalization of functional activation patterns, reorganization of functional connectivity, and normalization of brain metabolism following migraine treatment with external trigeminal neurostimulation, topiramate, and precision ophthalmic tints. (9-12) However, the effects of erenumab on brain function and structure, including the processing of painful stimuli, have been inadequately investigated. Furthermore, it is possible that measures of brain function and structure could serve as predictors for clinical response to erenumab, either prior to treatment or early after the first treatment. It is of clinical interest to interrogate whether neuroimaging is a useful technique for establishing a brain biomarker for predicting treatment response and measuring treatment responses earlier than is possible using clinical measures alone.

This study will investigate longitudinal changes in brain structure and function in high frequency episodic migraine and chronic migraine patients who are responding to erenumab treatment compared to those patients who are non-responders. In addition, pre-treatment and early post-treatment brain imaging data will be used to build models that predict which individual migraine patients will respond to erenumab treatment.

[figure not shown]
The Specific Aims of this study are to:

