## **Specific Aims**

- 1. Identify changes in brain function and structure that correlate with response to erenumab.** The objective of this aim is to investigate effects of treatment with erenumab on brain function and structure in patients who respond to treatment with erenumab and in patients who do not respond to treatment with erenumab. Specifically, this aim will assess changes in brain structure (cortical thickness, volume, area, white matter integrity), brain perfusion, resting-state functional connectivity, and pain-induced brain activation patterns in treatment responders and in treatment non-responders. This aim will identify structural and functional brain biomarkers for treatment response with erenumab.
- 2. Develop models to predict which patients will respond to erenumab.** The goal of this aim is to identify structural and functional brain magnetic resonance imaging predictors of response to erenumab in patients with migraine. Specifically, this aim seeks to identify those migraine patients who are going to have a positive response to erenumab treatment versus those who will not respond to treatment. Pre-treatment and early post-treatment imaging data will be used separately, and also in combination, for predictive modeling.

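### Aim 1 asks which brain changes go with response to erenumab, but the plan commits to no test that compares the change between responders and non-responders

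*Combined protocol and SAP*

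**What the plan says.** All of these are in the Combined protocol and SAP.

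- **What is to be learned.** The Aim 1 heading in Analysis Plans is to "identify changes in brain structure and function that correlate with response to erenumab". Specific Aims adds: "This aim will identify structural and functional brain biomarkers for treatment response with erenumab". Background promises to study longitudinal change in patients "who are responding to erenumab treatment compared to those patients who are non-responders". The primary hypothesis in the Summary links clinical improvement to normalization of brain function.
- **Primary analysis (Analysis Plans, Specific Aim #1).** It is the "comparison of pre-treatment pain-induced regional activation strength vs. post-treatment pain-induced regional activation strength in erenumab responders and separately in erenumab non-responders".
- **Region-of-interest analysis.** Regions found by comparison with healthy controls are used "to assess the longitudinal, within-group changes of erenumab responders and non-responders".
- **Mixed model.** "Within-group changes on cognitive measures, sensory testing and neuroimaging data will be assessed by applying a general linear mixed model design".
- **Between-group imaging comparison.** "Between subject group analyses will compare post-treatment MRI data in erenumab responders to non-responders".
- **Sample Size.** 21 per group gives 88% power for a pre-to-post BOLD difference of 0.1%, with SD 0.1 and type I error .05.

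**The concern.** The question is comparative, and the committed analyses of change are not. Two separate pre/post tests can give different significance verdicts when the two groups changed by the same amount. The post-treatment comparison is a between-group test, but not of change, and no baseline adjustment is stated. A baseline difference is plausible on the plan's own terms, because Aim 2 looks for features of the pre-treatment scan that separate responders from non-responders.

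Followed as written, the plan could present a region as tracking response when both groups changed equally, or when they differed before the first dose. The plan does not say it will draw that inference, but it commits to no test of change that would prevent it.

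**Working it through.** **1. Does another section supply the test?**

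| Section | What it offers | Why it does not close the gap |
|---|---|---|
| Analysis Plans, opening | within- and between-subject comparisons | the sentences that follow limit the between-group part to post-treatment data |
| Analysis Plans, methods sentence | general linear models for neuroimaging | no group-by-time term named |
| Daily Headache Diary | correlating change in migraine frequency with imaging | worded as optional |
| Follow up visits | week-8 markers that can be correlated with clinical response | a possibility, not a commitment |
| Imaging Data Plans | two-sample analysis of activation | cohorts unnamed; not stated to use change |
| Specific Aims, Aim 2 | "Pre-treatment and early post-treatment imaging data will be used separately, and also in combination, for predictive modeling" | predicts response from baseline and week-2 scans; does not test change to week 8 |

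**2. The stated 88%.** Inputs from Sample Size: n = 21 per group, difference 0.1, SD 0.1, alpha 0.05 (two-sided assumed). Power is from the noncentral t distribution.

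- Two-sample: ncp = 0.1 / (0.1 × √(2/21)) = 3.24, df 40, power 88.5%.
- Paired, SD of change 0.141: ncp = 0.1 / (0.141/√21) = 3.24, df 20, power 86.9%.
- Paired, SD of change 0.1: ncp = 4.58, power 99.2%.

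The 88% is therefore reproducible, but it lies close to two different tests. The text does not say which was powered, or whether the SD of 0.1 is per scan or of the change.

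**3. Responders-only significance when both groups truly change equally.** The groups are independent, so the probability is p(1 − p), where p is paired power at n = 21. SD of change = 0.1 × √(2(1 − ρ)), treating 0.1 as the per-scan SD. The values of ρ and the shared change of 0.05% are assumptions.

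| SD of change (ρ) | Shared change 0.05%: p, p(1 − p) | Shared change 0.1%: p, p(1 − p) |
|---|---|---|
| 0.1 (0.5) | 0.587, 24% | 0.992, under 1% |
| 0.1225 (0.25) | 0.429, 24% | 0.945, 5% |
| 0.141 (0) | 0.338, 22% | 0.869, 11% |

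With no change in either group the figure is 0.05 × 0.95 = 4.8%, which is the ordinary false-positive rate.

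Imaging Data Plans commits to multiplicity correction without giving a per-test level. With alpha 0.001 as a stand-in, the figures for the same three SDs are 9%, 5% and 3% at 0.05%, and 19%, 25% and 22% at 0.1%.

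**4. Post-only comparison with no drug effect.** Assume a baseline difference of 0.5 SD, 21 v 21. If it persists to week 8: ncp = 0.5/√(2/21) = 1.62, power 35%. Simulation with 40,000 trials per setting gives these rejection rates for ρ = 0.25 / 0.5 / 0.75:

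| Test | Difference persists | Difference regresses with ρ |
|---|---|---|
| Post-only | 35% / 35% / 35% | 7% / 13% / 22% |
| Change score | 5% / 5% / 5% | 16% / 12% / 9% |
| Baseline-adjusted ANCOVA | 22% / 14% / 9% | 5% / 5% / 5% |

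**5. Power of the missing contrast.** Two-sample t on change, 21 v 21, alpha 0.05, for SD of change 0.1 / 0.1225 / 0.141:

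- 0.1% difference in change: 88.5% / 73% / 61%.
- 0.05% difference in change: 35% / 25% / 20%.
- 0.1% difference, SD 0.1, alpha 0.001: 39%.

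**The case against.** - **The within-group tests fit part of the objective.** Specific Aims also says change will be assessed in responders and in non-responders, and two pre/post analyses answer that. This stands, but it does not cover correlation with response or the biomarker claim.
- **The intent and the model family are present.** Background promises a comparison, and linear and mixed models are planned, so this could be read as an unspecified contrast. That makes the repair easy. However, the text expressly restricts the mixed model to within-group change and the group comparison to post-treatment data.
- **The harm is conditional and the sizes are assumed.** Both are true. The shared change of 0.05% and the baseline difference of 0.5 SD are not in the documents, and at 0.1% with SD of change 0.1 the uncorrected figure is under 1%. At alpha 0.001, however, the problem moves to the planned 0.1% effect (19% to 25%) and does not disappear.
- **A change-score contrast is not always the better test.** This stands. If the baseline difference regresses, its false-positive rate is 9% to 16%: worse than post-only at ρ = 0.25 and about equal at 0.5. The contrast therefore needs ANCOVA beside it.
- **The power basis is a separate matter.** Partly so. It belongs here because adding the contrast means naming the test that is powered.

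**Conclusion.** The concern holds, and the plan must be changed on this point. As written, it does not test its own Aim 1: no committed analysis compares change between responders and non-responders.

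The omission follows from the text and needs no assumption. Its size does: the figures are for a single region, at uncorrected 0.05 unless stated, and rest on the assumed shared change, SD of change and baseline difference. The stated 88% power is not an arithmetic error, but it does not identify the test.

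**What to change.** **Analysis Plans, Specific Aim #1**

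- Add a responder-group by time contrast (baseline to week 8) to the planned mixed model, under the multiplicity correction in Imaging Data Plans. Make it the test on which any claim of association with response rests.
- Keep both within-group comparisons, reported as estimates with confidence intervals. Label the post-treatment comparison descriptive.
- Commit to regressing activation change on change in migraine days as the supporting analysis.
- Report baseline-adjusted ANCOVA as a sensitivity analysis, because which method is unbiased depends on whether a baseline difference persists or regresses.
- State as limits that regression to the mean and other effects not shared by the groups remain in an open-label, non-randomised study, and that normalization still rests on the healthy-control comparison.

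**Sample Size**

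- Name the test being powered, and give power for the contrast with an explicit SD of change.

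**Cost.** Wording and a restated power statement; no new scans or visits. The real price is lower power: for 0.1%, the contrast has 88.5%, 73% or 61%, against 99%, 95% or 87% for the paired within-group test at the same SDs of change. The change should be made before outcome data are seen, because a contrast chosen afterwards would be post hoc.
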